#### 2. LIST OF ABBREVIATIONS

Term	Definition / description
AE	Adverse Event
AESI	Adverse Event of Special Interest
ANCOVA	Analysis of Covariance
CIAS	Cognitive Impairment Associated with Schizophrenia
C-SSRS	Columbia Suicidality Severity Rating Scale
СТР	Clinical Trial Protocol
ICE	Intercurrent Event
iPD	Important Protocol Deviation
MATRICS	Measurement and Treatment Research to Improve Cognition in Schizophrenia
MCCB	MATRICS Consensus Cognitive Battery
MedDRA	Medical Dictionary for Drug Regulatory Activities
MI	Multiple Imputation
MMRM	Mixed-effects Model for Repeated Measures

PK Pharmacokinetics

Patient Reported Experience of Cognitive Impairment in Schizophrenia **PRECIS** 

Penn Physician Withdrawal Checklist PWC-20

REML Restricted Maximum Likelihood

REP Residual Effect Period

Term	Definition / description
SCoRS	Schizophrenia Cognition Rating Scale
ToL	Tower of London
VRFCAT	Virtual Reality Functional Capacity Assessment Tool

#### 3. INTRODUCTION

As per International Conference on Harmonisation (ICH) E9, the purpose of this document is to provide a more technical and detailed elaboration of the principal features of the analysis described in the protocol, and to include detailed procedures for executing the statistical analysis of the primary and secondary variables and other data.

This Trial Statistical Analysis Plan (TSAP) assumes familiarity with the Clinical Trial Protocol (CTP), including Protocol Amendments. In particular, the TSAP is based on the planned analysis specification as written in CTP Section 7 "Statistical Methods and Determination of Sample Size". Therefore, TSAP readers may consult the CTP for more background information on the study, e.g., on study objectives, study design and population, treatments, definition of measurements and variables, planning of sample size, randomization.

SAS® Version 9.4 will be used for all analyses if not otherwise specified. Pheonix WinNonlinTM Version 8.1 will be used for pharmacokinetic (PK) analyses.

## 4. CHANGES IN THE PLANNED ANALYSIS OF THE STUDY

For the further endpoint of change from screening Visit 1a in PRECIS individual items and domain scores at Week 24, only the PRECIS domain scores will be analyzed, and the PRECIS individual items will not be analyzed.

Definition of baseline for the assessments of efficacy, and C-SSRS will include assessments up to but no later than the day of the first administration of study medication.

# 5. ENDPOINTS(S)

#### 5.1 PRIMARY ENDPOINT(S)

The primary endpoint is

• Change from baseline in MCCB overall composite T-score at Week 26.

MCCB assessments are planned to be performed at screening (Visit 1), baseline (Visit 2), Week 12 (Visit 6), and Week 26 (Visit 11/EOT) or any early end of treatment visit.

Any post-baseline MCCB assessments performed within 28 days of the previous assessment will be considered invalid because of potential practice effects and will be excluded prior to any subsequent data handling and therefore from the planned analyses (5).

The MCCB overall composite T-score will be derived from seven domain scores from a total of ten tests (see CTP Table 5.1: 1). A larger MCCB overall composite T-score indicates better cognition.

## 5.2 SECONDARY ENDPOINT(S)

## 5.2.1 Key secondary endpoint(s)

The key secondary endpoints are:

- Change from baseline in Schizophrenia Cognitive Rating Scale (SCoRS) interviewer total score at Week 26
- Change from baseline in Virtual Reality Functional Capacity Assessment Tool (VRFCAT) adjusted total time T-score at Week 26.

A lower rating in SCoRS reflects a lesser degree of impairment. A higher T-score in VRFCAT indicates a better functional outcome.

The endpoints will be used as defined in CTP Section 5.

[figure not shown]
#### 5.2.2 Secondary endpoint(s)

[figure not shown]
The other secondary endpoints are:

[figure not shown]
- Change from baseline in the T-score of the number of correct responses on Tower of London (ToL) at Week 26
- Change from screening Visit 1a in Patient Reported Experience of Cognitive Impairment in Schizophrenia (PRECIS) total score at Week 24

A higher T-score in ToL indicates a better outcome. A lower score in PRECIS corresponds to a better patient experience.

The endpoints will be used as defined in CTP Section 5.

#### 6. GENERAL ANALYSIS DEFINITIONS

## 6.1 TREATMENT(S)

For basic study information on treatments to be administered, assignment of treatment groups, select of doses, see CTP Section 4.

Table 6.1: 1 lists the two treatment groups in this study. Table 6.1: 2 defines the analysing treatment period for safety analyses. For this study, the residual effect period (REP) is defined as 12 days after the last dose of trial medication.

Table 6.1: 1 Treatment descriptions

Long Name	Short Name	
Placebo	Placebo	
Iclepertin 10 mg QD	Iclepertin 10 mg	

Table 6.1: 2 Analysing treatment periods (same for all treatment groups)

Analysing Treatment Period	Start Date	End Date
Screening period	Date of informed consent	Date of the first treatment administration – 1 day
On-treatment period	Date of the first treatment administration	Date of the last treatment administration + REP
Post-treatment period	Date of the last treatment administration + REP + 1 day	Date of the last per protocol visit
Strictly on-treatment period	Date of the first treatment administration	Date of the last treatment administration
4-week withdrawal period	Date of last treatment administration + 1 day	Date of last treatment administration + 28 day

REP is the residual effect period which is defined as 12 days after the last dose of trial treatment.

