- ¹⁴ For patients not rolling over to the extension study: after the individual patient's end of the study, the investigator should report only any cancers of new histology and exacerbations of existing cancer, trial treatment related SAEs and trial treatment related AESIs of which the investigator may become aware of and only via the BI SAE form, please see section 5.2.6.2.1.
- ¹⁵ Duration of visits indicated in this Flow Chart are approximate estimates, actual time may vary as per site and patient requirements.
- ¹⁶ Visit 11 will be performed only by patients who prematurely discontinue trial drug but agree to continue trial participation. For patients who have permanently discontinued study medication the following procedures are no longer required: Dispense and administer IMP, IMP compliance check, AiCure review, PK Sampling, bio banking sampling.
- ¹⁷ If the patient permanently discontinues treatment early, the eEOT visit must be performed within 7 days of study drug discontinuation. The patient should be followed up according to guidance provided in section 6.2.3.4. For patients who permanently discontinue study medication the following procedures do not need to be performed: Dispense and administer IMP, IMP compliance check, AiCure review, PK Sampling, bio banking sampling and Physician Withdrawal Checklist at visit 10. For follow up of patients with Hb related issues, please refer to section 5.2.6.4
- 18 Safety follow-up visits must be completed after the EOT or early EOT visit. Each follow-up visit is to be scheduled from the EOT or early EOT visit (e.g. follow-up visit 1 should be conducted 7 days \pm 1 day from the EOT or early EOT visit).
- ¹⁹ Patients who finish the 26 weeks of treatment period in this study and the 4 weeks of safety follow-up, can rollover to the extension trial after completing follow-up visit 6.
- ²⁰ Study partner must complete the SCoRS and interviews at least at Visit 2 and EOT (please refer to inclusion criterion # 8)
- ²¹ Additional collection of the C-SSRS at an unscheduled visit may be done based on the investigator's discretion.
- X^H Haematology panel A and B only.

Page 8 of 112

Page 9 of 112

Proprietary confidential information © 2023 Boehringer Ingelheim International GmbH or one or more of its affiliated companies

TA	RI	\mathbf{F}	OF	CO	N	$\Gamma \Gamma N$	JTC
-1	DL	ינונ	v	,		יוניו	

TITLE I	PAGE	1
CLINIC	AL TRIAL PROTOCOL SYNOPSIS	2
FLOW (CHART	6
TABLE	OF CONTENTS	9
ABBRE	VIATIONS	13

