4.1.4 Drug assignment and administration of doses for each patient

Dispensing of medication kits for the double-blind treatment period will begin at Visit 2. Throughout the treatment period, 2 trial medication kits will be provided at each visit. Medication assignment will be provided through IRT. The assigned medication kit numbers must be entered in the eCRF, and the corresponding medication kits must be given to the patient. The duration of treatment is 26 weeks. At each of the visits, patients will receive supplies for a total of 4 weeks.

The first dose of study medication will be taken at the end of Visit 2 under supervision of the investigator or delegated site staff, after all Visit 2 assessments have been completed. In case the Visit 2 is split into 2 sequential days, the first dose of study medication should be taken on the second day of the split visit, after all Visit 2 assessments have been completed.

Throughout the study, patients should be instructed to take 1 tablet orally with water and with or without food after waking up. If a dose is missed by more than 12 hours, that dose should be skipped and the next dose should be taken as scheduled.

Patients should be instructed **not** to take their study medication at home on the day of the clinic visit as patients will be dosed at the site. Dosing should occur approximately 24 hours after the drug administration from the preceding day.

Page 44 of 112

Proprietary confidential information © 2023 Boehringer Ingelheim International GmbH or one or more of its affiliated companies

The last dose of study medication should be taken on the day before the EoT Visit. In case the EoT Visit is split into 2 sequential days, the last dose of study medication should be taken on the day before the first day of the split visit.

On longer visit days the dosing may occur in the afternoon.

A dose reduction of Iclepertin is not possible.

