- Any abnormal condition of clinical significance identified, during physical examination, vital signs, 12 lead ECG, laboratory assessment or any other medical assessment should be recorded as a baseline condition, if noted at screening, or as an AE if noted during treatment or follow up period, as applicable.
- Safety labs (including urinalysis) and/or urine drug screen, may be performed more frequently based on investigator discretion or if required locally.
- Patients do not have to come fasted for any trial visits.

Study partner requirements:

- The study partner should remain constant throughout the trial period, however in exceptional circumstances, a change of study partner will be allowed.
- Input from study partners will be required on the assessments indicated in the Flow Chart.
- In-person ratings are preferred whenever possible. However, if the study partner is not available for in-person ratings, telephone interview is acceptable. The telephone interview with the study partner must be conducted within the visits window indicated in the Flow Chart for which study partner input on SCoRS, required.

For study partners who also serve are also caregivers:

	Please refer to Appendix 10.2 for definition of	f study
partner vs. caregiver.		

• For caregiver assessments, in-person visit is preferred. However, if not possible, the caregiver may come on another day to fill-in the this should be as close to the visit as possible, preferably within the study visit window.

COVID-19 specific instructions:

During the COVID-19 pandemic, there might be situations when patients already in the study might not be able to come to the site for the scheduled visit. This might be due to restrictions set by authorities or by the investigator site/institution, because the patient is quarantined, or because of any patient specific situation that the investigator judges as being not safe for the patient to come to the site. For details on potential modifications of the trial conduct related to the COVID-19 pandemic, please refer to Appendix 10.3.

Page 71 of 112

Proprietary confidential information © 2023 Boehringer Ingelheim International GmbH or one or more of its affiliated companies

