In addition to the main safety analysis, withdrawal-related safety analysis will be conducted separately and descriptive for AEs emerging during the off-treatment safety follow-up period. New AEs emerging during this 4-week safety period, compared to while the patient is still on-treatment, will be identified and assessed by contrasting the following analysing treatment periods:

- 4-week withdrawal period for AEs occurring from 1 day after last dose to 28 after last dose of trial medication, and
- Strictly on-treatment period for AEs occurring from the start of treatment to the last dose of trial medication.

Page 84 of 112

Proprietary confidential information © 2023 Boehringer Ingelheim International GmbH or one or more of its affiliated companies

This withdrawal-related safety analysis will also assess vital signs descriptively.

Change in withdrawal symptoms based on PWC-20 will be analysed descriptively.

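### For completers, the EOT visit is Day 1 of the 4-week withdrawal period, so clinically relevant AEs dated to that visit count as withdrawal events in one descriptive contrast (minor)

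*SAP*

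**What the plan says.** Protocol 7.2.5 plans a separate descriptive analysis of "AEs emerging during the off-treatment safety follow-up period". It contrasts two periods:

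- "Strictly on-treatment period for AEs occurring from the start of treatment to the last dose of trial medication"
- "4-week withdrawal period for AEs occurring from 1 day after last dose to 28 after last dose of trial medication"

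SAP Table 6.1: 2 gives the same withdrawal window, from "Date of last treatment administration + 1 day" to "Date of last treatment administration + 28 day". The protocol and SAP agree on these dates.

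The timing of the visit is set elsewhere. Protocol 4.1.4 states: "The last dose of study medication should be taken on the day before the EoT Visit". If the visit is split over two days, the last dose falls on the day before the first of them. The Flow Chart places EOT/Visit 11 in the randomized treatment period, and its footnote 18 says: "Safety follow-up visits must be completed after the EOT or early EOT visit".

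The EOT visit includes physical examination, vital signs, ECG and safety laboratory tests. Under Protocol 6.2.1, an abnormal finding of clinical significance is recorded as a baseline condition if noted at screening, "or as an AE if noted during treatment or follow up period, as applicable".

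**The concern.** The contrast is meant to show which adverse events emerge once the drug is stopped. Protocol Table 1.4.2:1 says that such events have not been formally investigated so far, so the table will be read with some attention.

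Events found by scheduled examination cluster on examination days, and here a full examination falls on the first withdrawal day. At earlier visits patients also arrive before that day's dose, about 24 hours after the previous one (Protocol 4.1.4), so a completer at EOT is in the same pre-dose state as at an on-treatment visit. A finding that arose on drug but was first seen at EOT would leave the on-treatment side and enter the withdrawal side. If such findings were more frequent on iclepertin, part of an on-drug effect could look like an effect of stopping.

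**Working it through.** **Inputs.** Day 1 is the first dose (SAP 6.7). EOT is planned at Week 26. Last dose is EOT − 1 day (Protocol 4.1.4). The withdrawal period runs from last dose + 1 to last dose + 28, and the residual effect period (REP) is 12 days (SAP Table 6.1: 2).

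**Dates for an on-schedule completer**

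1. Planned EOT day: 26 × 7 + 1 = 183. This reproduces Day 183 in the Flow Chart and SAP Table 6.7: 1.
2. Last dose: 183 − 1 = Day 182.
3. Strictly on-treatment period: Day 1 to Day 182.
4. Withdrawal period: 182 + 1 = Day 183 to 182 + 28 = Day 210. EOT is its first day.
5. Main on-treatment period: ends on 182 + 12 = Day 194, so EOT lies inside it.

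**Visit window (±3 days) and split visits**

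| EOT day | Last dose | Withdrawal period | EOT inside? |
|---|---|---|---|
| 180 | 179 | 180–207 | yes |
| 183 | 182 | 183–210 | yes |
| 186 | 185 | 186–213 | yes |

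For a visit split over Days 183 and 184, both days are inside.

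**Which findings could first appear at EOT?** From the Flow Chart and Protocol Table 5.2.3:1:

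- ECG, physical examination and vital signs were last scheduled at Visit 8 (Day 127): 183 − 127 = 56 days earlier. SAP 7.8.4 reports clinically relevant ECG abnormalities as AEs.
- Prolactin was last scheduled at Visit 2 (Day 1): 183 − 1 = 182 days earlier.
- Haematology is also taken at Visits 8, 9 and 10 (Days 127, 148 and 169), the last only 183 − 169 = 14 days earlier.

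**How the SAP treats the same visit elsewhere.** Tables 6.7: 7 and 6.7: 8 map laboratory values, weight and vital signs from Day 176 onward to on-treatment Visit 11, cut off only at the end of the REP. Table 6.7: 10 labels withdrawal-checklist values less than 7 days after the last dose as the last on-treatment value. A prolactin value drawn at EOT is therefore on-treatment, while an AE based on it and dated to that day is a withdrawal AE.

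**Patients exposed to the rule.** Protocol 7.5 projects 30% to 40% early treatment termination: 586 × 0.60 = 351.6, about 352; 586 × 0.70 = 410.2, about 410. Both arms are combined, and every completer is assumed to follow the dosing instruction.

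**Early terminators.** Their eEOT visit is due within 7 days of the last dose (Protocol 6.2.3.4) and has the same kinds of examination. At 1 to 7 days after the last dose it also falls inside the withdrawal period.

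**The case against.** The boundary can be defended. Protocol and SAP give identical windows, and dividing dosed from undosed days is a coherent rule that applies equally to both arms. The Flow Chart governs scheduling and does not define AE analysis periods. This much stands: the documents do not disagree on the dates. The tension is between the boundary and the stated purpose of the analysis, and with how the SAP classes other data from the same visit.

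A reader might infer that all abnormal EOT findings become withdrawal AEs. The documents do not support that. Only findings judged clinically relevant, newly reported as AEs and given an onset on the EOT date are affected; an AE with earlier onset stays where it was.

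A reader might also infer that on-treatment events are lost from the safety analysis. They are not. AEs up to last dose + 12 days are treatment-emergent in the main tables, and the withdrawal contrast involves no hypothesis test.

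Nor is a fall in haemoglobin a good example. Haematology is taken at three visits in the eight weeks before EOT, the haemoglobin-related values are withheld from sites, and the first two of the three alerts in Protocol 5.2.6.4 do not by themselves require an AE report.

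Finally, if the REP makes Day 1 effectively on-drug, the same could be said of Days 2 to 12, and the plan accepts that overlap. This is fair as pharmacology. The reason to treat Day 1 differently is the scheduled examination. The next on-site visit, Follow-up 2, is at EOT + 14 ± 1 day, so no earlier than 183 + 14 − 1 = Day 196, after the REP ends on Day 194. For a completer, EOT is thus the only scheduled on-site examination in the overlap.

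**Conclusion.** The point holds, at minor severity. For any completer who follows Protocol 4.1.4, the EOT visit is Day 1 of the withdrawal period, whatever the visit window or split. Clinically relevant findings first detected there and dated to that day are placed on the withdrawal side by rule. ECG, physical examination and prolactin are the plausible sources.

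The consequence is possible misattribution within one descriptive contrast. No efficacy result, hypothesis test or main safety table changes.

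About 352 to 410 patients are exposed to the rule, but the number with such an AE cannot be derived from the documents. Assumed rates of 2% to 5% would give 0.02 × 352 = 7 to 0.05 × 410 = 20.5, about 7 to 21 patients; nothing in the plan supports those rates. A reader might also posit a difference between arms, say 3% against 1%, and infer a 2-point false excess on iclepertin. That excess would be an input, not a result.

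The conclusion assumes that AE onset is dated to the day of the finding. The sponsor's AE guides cited in the SAP are not part of these documents.

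**What to change.** In SAP Table 6.1: 2 and Protocol 7.2.5, state that when EOT is the day after the last dose, AEs with onset on the EOT visit date (both days of a split visit) count as strictly on-treatment. The withdrawal period then starts on the next day: last dose + 2, or last dose + 3 after a split visit. For an on-schedule completer, and with the end of the period left unchanged, it runs from Day 184 to Day 210, or from Day 185 after a split visit.

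Also state how AEs dated to an eEOT visit are assigned, for example by flagging them separately. Otherwise completers and early discontinuers would have different windows with no explanation.

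The cost is one line in the SAP table, a matching clarification in the protocol and a sentence on eEOT; no new data are needed. The downside is that a genuine withdrawal AE starting on the EOT date would be counted as on-treatment. With a 12-day residual effect period this should be uncommon, and a listing of AEs dated to the EOT visit would keep it visible.

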#### 6.2 IMPORTANT PROTOCOL DEVIATIONS

Handling of iPDs in analyses is described in the iPD specification document and stored in the Trial Master File (TMF) in the electronic Document Management System (eDMS).

#### 6.3 INTERCURRENT EVENTS

Definition and technical specification of protocol defined intercurrent events (ICEs) are listed in Table 6.3: 1. In general, when handled under the hypothetical approach, data collected during the off-treatment period of an ICE will be considered irrelevant to the estimand and excluded from the analysis. While off-treatment data will be excluded, the patient will still be

considered as on-treatment (hypothetically) from an analysis perspective by the statistical models, and during any imputations.

For an ICE of temporary treatment discontinuation or interruptions, the off-treatment period spans from the last treatment administration prior to the interruption + REP to the restart of the study medication. For an ICE of early permanent treatment discontinuation, the off-treatment period starts from the last treatment administration + REP. Figure 6.3: 1 illustrates the on-/off-treatment status after each type of ICEs. When there is more than one ICE of early permanent treatment discontinuation, any treatment policy ICE take precedence in data and analysis handling over any hypothetical ICE.

ICEs of change in concomitant therapies and other ICEs will always be considered as part of the treatment policy in the primary and all supplementary estimands. ICEs of this category will not affect the on-/off- treatment status which is only determined by changes in the study medication. These ICEs will be listed and summarized descriptively but will not be explicitly accounted for in the inferential analysis of efficacy.

Table 6.3: 1 Definition and technical specification of intercurrent events

[figure not shown]
Type of Intercurrent Event	Definition and Documentary Sources	Handling under the Primary Estimand
Temporary Tr	reatment Discontinuations or Interruption	ons
Exacerbation or acute episode of schizophrenia resulting in interruption of treatment	Identified from data collected in the Temporary Trial Treatment Discontinuation and Adverse Event pages of the CRF:  - Temporary discontinuation of trial treatment reported with reason being "Adverse Event", and  - AE category reported as "Schizophrenia Relapse" or MedDRA preferred term coded as "Schizophrenia"	Treatment policy
Temporary treatment discontinuation or interruption due to other reasons	Identified from data collected in the Temporary Discontinuation page of the CRF.	Hypothetical – only data collected from the end of REP after the interruption, to end of the interruption will be subject to exclusion from the analysis
Temporary treatment-switch	Identified from the dispensation records. Temporary treatment-switch will be handled as temporary interruptions in the same way for	Hypothetical – only data collected from the end of REP after the treatment switch, to end of the

due to dispensation error	both directions (iclepertin to placebo or placebo to iclepertin)	treatment switch will be subject to exclusion from the analysis			
Early Perman	Early Permanent Treatment Discontinuation				
Exacerbation or acute episode of schizophrenia resulting in early termination of treatment	Identified from data collected in the Adverse Event page of the CRF:  - "Drug Withdrawn" reported in the Action Taken with Study Treatment field, and  - Category reported as "Schizophrenia Relapse" or MedDRA preferred term coded as	Treatment policy			
Investigator assessed drug- related adverse events which lead to early termination	"Schizophrenia"  Identified from data collected in the Adverse Event page of the CRF:  - "Drug Withdrawn" reported in the Action Taken with Study Treatment field, and	Treatment policy			
of study medication	- "Yes" reported in the Relationship to Study Treatment field				
Protocol-defined drug withdrawal due to treatment – haemoglobin decrease	Identified from data collected in the End of Treatment and Adverse Event pages of the CRF and laboratory data:  - Subject who did not complete the planned treatment period as reported in the End of Treatment page with reason being "Adverse Event", and  - AE indicating haemoglobin decrease with action taken being "Drug Withdrawn"	Treatment policy			
Protocol-defined drug withdrawal due to treatment – CYP3A4 inhibitors or CYP3A4 sensitive drugs with NTI	Identified from data collected in the End of Treatment page of the CRF:  - Subject who did not complete the planned treatment period as reported in the End of Treatment page with "Protocol Deviation" as the reason, and  - Use of CYP3A4 inhibitors or CYP3A4 sensitive drugs with	Treatment policy			

	NTI specified as the detailed reason of discontinuation	
Early termination of study	Identified from data collected in the End of Treatment page of the CRF:	Hypothetical
medication due to other AEs	- Subject who did not complete the planned treatment period as reported in the End of Treatment page with reason being "Adverse Event" and not otherwise covered by any of the ICEs above.	
Early termination of study medication due to perceived lack of	Identified from data collected in the End of Treatment page of the CRF:  - Subject who did not complete the planned treatment period as	Hypothetical
efficacy	reported in the End of Treatment page with reason being "Perceived Lack of Efficacy".	
Early termination of study	Identified from data collected in the End of Treatment page of the CRF:	Hypothetical
medication due to other reasons	- Subject who did not complete the planned treatment period as reported in the End of Treatment page for reasons not covered by any of the ICEs above.	
Change in Co	ncomitant Therapies and Other ICEs	
Change in background medication	Identified from data collected in the Concomitant Medications page of the CRF:  - Start of a new or stop of an ongoing antipsychotic, benzodiazepines (or derivatives),	Treatment policy
	anticholinergics, antiepileptics, or antidepressants during the on- treatment period, or	
	- Change of dosage or dosing frequencies of an on-going antipsychotic, benzodiazepines (or derivatives), anticholinergics, antiepileptics, or antidepressants during the on-treatment period	
	See Table 10.7: 1 for definitions of antipsychotics, benzodiazepines (or	

	derivatives), anticholinergics, antiepileptics, and antidepressants.	
Change in psychotherapy	Identified from data collected in the Psychotherapy page of the CRF:	Treatment policy
	- Change in frequency, setting or session of a psychotherapy during the on-treatment period	
Change in other non-pharmacological	Identified from data collected in the Concomitant Non-Drug Therapies page of the CRF:	Treatment policy
therapy	- Start of a new non-drug therapy or stop of an on-going non-drug therapy during the on-treatment period	
Change in study partner in the assessment of functional capacity,	Identified from data collected in the Study Partner Informed Consent page of the CRF and date/time of SCoRS assessments:	Treatment policy – relevant only to endpoints from the SCoRS assessment
e.g. SCoRS	- Any new study partner informed consent signed between the baseline SCoRS assessment and the SCoRS assessment being considered	

Figure 6.3: 1 On-/off-treatment status of the study medication for efficacy analysis after ICEs

